5.1 Imputation rules

5.1.1 Study treatment

The following rules should be used for the imputation of the dose end date for a given study treatment component:

Scenario 1

If the date of last IVT is completely missing and there is no end of treatment (EOT) page and no death date, the patient is considered as on-going.

The patient should be treated as on-going and the cut-off date should be used as the last dosing date.

Scenario 2

If the dose end date is completely or partially missing and the EOT page is available:

- Case 1: The dose end date is completely missing and the EOT completion date is complete, then this latter date should be used.
- Case 2: Only year (YYYY) of the dose end date is available and YYYY < the year of EOT date, then use 31DECYYYY.
- Case 3: Only year (YYYY) of the dose end date is available and YYYY = the year of EOT date, then use EOT date.
- Case 4: Both year (YYYY) and month (MMM) are available for dose end date and YYYY = the year of EOT date and MMM < the month of EOT date, then use last day of the Month (MMM)

All other cases should be considered as a data issue and the statistician should contact the data manager of the study.

After imputation, compare the imputed date with start date of treatment.

If the imputed date is < start date of treatment, then use the treatment start date.

Otherwise, use the imputed date

Patients with missing start dates are to be considered missing for all study treatment component related calculations and no imputation will be made. If start date is missing then end-date should not be imputed.

5.1.2 AE date imputation

AE date imputation is based only on a comparison of the partial AE start date to the treatment start date as mentioned in the below.

1. If the AE start date year value is missing, the date uncertainty is too high to impute a rational date. Therefore, if the AE year value is missing, the imputed AE start date is set to NULL.
2. If the AE start date year value is less than the treatment start date year value, the AE started before treatment. Therefore:
 - a. If the AE year is less than the treatment year and the AE month is missing, the imputed AE start date is set to the mid-year point (01JulYYYY).
 - b. Else if the AE year is less than the treatment year and the AE month is not missing, the imputed AE start date is set to the mid-month point (15MONYYYY).

3. If the AE start date year value is greater than the treatment start date year value, the AE started after treatment. Therefore:
 - a. If the AE year is greater than the treatment year and the AE month is missing, the imputed AE start date is set to the year start point (01JanYYYY).
 - b. Else if the AE year is greater than the treatment year and the AE month is not missing, the imputed AE start date is set to the month start point (01MONYYYY).
4. If the AE start date year value is equal to the treatment start date year value:
 - a. And the AE month is missing or the AE month is equal to the treatment start month, the imputed AE start date is set to one day after treatment start.
 - b. Else if the AE month is less than the treatment start month, the imputed AE start date is set to the mid-month point (15MONYYYY).
 - c. Else if the AE month is greater than the treatment start month, the imputed AE start date is set to the start month point (01MONYYYY).

	MON		MON < CFM		MON = CFM		MON > CFM					
	MISSING											
YYYY MISSING	NULL		NULL		NULL		NULL					
	Uncertain		Uncertain		Uncertain		Uncertain					
YYYY < CFY	(D) = 01JULYYYY		(C)= 15MONYYYY		(C)= 15MONYYYY		(C)= 15MONYYYY					
	Before Treatment Start		Before Treatment Start		Before Treatment Start		Before Treatment Start					
YYYY = CFY	(B)= TRTSTD+1		(C)= 15MONYYYY		(A)= TRTSTD+1		(A)= 01MONYYYY					
	Uncertain		Before Treatment Start		Uncertain		After Treatment Start					
YYYY > CFY	(E)= 01JANYYYYY		(A)= 01MONYYYY		(A)= 01MONYYYY		(A)= 01MONYYYY					
	After Treatment Start		After Treatment Start		After Treatment Start		After Treatment Start					
Before Treatment Start			Partial indicates date prior to Treatment Start Date									
After Treatment Start			Partial indicates date after Treatment Start Date									
Uncertain			Partial insufficient to determine relationship to Treatment Start Date									
LEGEND:												
(A)		MAX(01MONYYYY,TRTSTD+1)										
(B)		TRTSTD+1										
(C)		15MONYYYY										
(D)		01JULYYYY										
(E)		01JANYYYYY										

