 - Concomitant medication or non-drug therapy given
 - Patient hospitalized/patient's hospitalization prolonged (see [Section 10.1.2](#) for definition of SAE)
6. Its outcome:
 - Not recovered/not resolved
 - Recovered/resolved
 - Recovered/resolved with sequelae
 - Fatal or unknown.
7. Its location (ocular event/non ocular event)

Conditions that were already present at the time of informed consent should be recorded in the medical history of the patient.

Adverse events (including lab abnormalities that constitute AEs) should be described using a diagnosis whenever possible, rather than individual underlying signs and symptoms.

Adverse event monitoring should be continued until 30 days (safety follow-up) after the last administration of study treatment (see “Post-treatment follow-up period” in [Section 3](#)).

Once an AE is detected, it must be followed until its resolution or until it is judged to be permanent (e.g. continuing at the end of the study), and assessment must be made at each visit (or more frequently, if necessary) of any changes in severity, the suspected relationship to the interventions required to treat it, and the outcome.

Information about adverse drug reactions for the investigational drug can be found in the IB.

Abnormal test results constitute AEs only if they fulfill at least one of the following criteria:

- they induce clinical signs or symptoms
- they are considered clinically significant
- they require therapy

Clinically significant abnormal test results must be identified through a review of values outside of normal ranges/clinically notable ranges, significant changes from Screening/Baseline or the previous visit, or values which are considered to be non-typical in patients with the underlying disease. Investigators have the responsibility for managing the safety of individual patients and identifying AEs.

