12.5.5 Safety endpoints

The Safety Set will be used for all safety analyses.

The secondary safety endpoint of this study is as follows:

- Incidence of AEs (serious and non serious) reported in patients treated with brolucizumab.

Safety summaries (tables, figures) include only data from the on-treatment period with the exception of Baseline data, which will also be summarized where appropriate (e.g. change from Baseline summaries). In addition, a separate summary for death including on treatment and post treatment deaths will be provided. In particular, summary tables for adverse events of special interest (AESIs) will summarize only on-treatment events, with a start date during the on-treatment period (treatment-emergent AEs).

The on-treatment period lasts from the date of first administration of IVT injection of study treatment to 30 days after the date of the last actual administration of IVT injection of study treatment.

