12.5.5.1 Adverse events

Summary tables for AEs will summarize only on-treatment events with start date during the on-treatment period. Separate summary tables will be provided for AEs of the study eye, the fellow eye, and for non-ocular AEs.

The on-treatment period lasts from the date of first administration of study treatment to 30 days after the last administration of study treatment or EOS whichever is the latest.

All information obtained on AEs will be displayed by patient. All collected AEs will be listed.

[figure not shown]
The number (%) of patients with treatment-emergent AEs will be summarized in the following ways:

- by visit, primary system organ class and preferred term.
- by visit, primary system organ class, preferred term and maximum severity.

Separate summaries will be provided for AEs related to study medication, deaths, SAEs, AESIs and other AEs leading to discontinuation.

The number (%) of patients with AEs of special interest will be summarized by visit, primary system organ class and preferred term.

A patient with multiple AEs within a primary system organ class will only be counted once towards the total of the primary system organ class.

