Percent change from Baseline: The percent change from baseline will be calculated as below: $((\text{post-baseline value} - \text{Baseline value}) / \text{Baseline value}) * 100$.

Proportion: A proportion refers to the fraction of the total that possesses a certain attribute. In this study attribute is disease free activity.

Disease control: When patients have no disease activity after taking study treatment then patient will be consider as disease control.

On-treatment period: The on-treatment period lasts from the date of first administration of study treatment to 30 days after the date of the last actual administration of any study treatment.

Treatment duration: The maximum planned duration of treatment for each patient is 44 to 46 weeks in accordance with the designated treatment regimen. Discontinuation of study treatment for a patient occurs when study treatment is stopped earlier than the protocol planned duration and can be initiated by either the patient or the investigator.

Treatment discontinuation: When patients discontinue study treatment but continue in the study, the efficacy data will be used at the time the patient stopped study treatment.

Last interval: The last treatment interval (defined by the investigator) before Week 48.

Maximum interval: The longest interval of treatment reached by the patient over the study period.

Event for no disease activity: When patients will be with no disease status as per investigator decision after last dose in initiation phase then the patients will consider as event for no disease activity. If patients with active disease status or early discontinue then patients will be considered as censored for disease activity.

Dry retina: Absence of fluid (IRF/SRF/ sub-RPE) will be considered as dry retina.

Event for dry retina: When patients have absence of fluid then it will be considered as an event of dry retina. If patients have a presence of fluid before/at EOS or early discontinuation then will be censored.

[figure not shown]
Study eye and fellow eye: The investigator selects the eye with the worse BCVA at Screening as the study eye if both eyes are eligible as per the inclusion and exclusion criteria, unless the investigator deems as a study eye more appropriate to select the eye with better BCVA, based on medical reasons or local ethical requirements. If both eyes are eligible as per the inclusion and exclusion criteria, then it is recommended to select the right eye as the study eye.

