2.9.1 Adverse events

All information obtained on AEs will be displayed by patient Summary tables for AEs will summarize only on-treatment events, with a start date during the on-treatment period ([see Section 2.1.1](#)) for definition of on-treatment period).

The count of treatment-emergent AEs, number (and percentage) of patients with treatment-emergent AEs (defined as events started after the first dose of study treatment or events present prior to start of study treatment but increased in severity based on PT) will be summarized in the following ways:

- By primary SOC and PT.
- By primary SOC, PT and maximum severity.

Separate summaries will be provided for study treatment related AEs, study procedure related AEs, need of USM, death, SAEs, other significant AEs action taken leading to study treatment withdrawn and AEs leading to dose interval adjustment (interval increase, interval reduce).

Adverse events will be summarized by presenting, the number and percentage of patients having any AE, having an AE in each primary SOC and having each individual AE (PT). Summaries will also be presented for AEs by severity. Summaries for AE will be presented for study treatment and procedure related to AEs. If a patient reported more than one AE with the same PT, the AE with the greatest severity will be presented. SOC will be presented in alphabetical order, preferred terms will be sorted within SOC in descending frequency of AEs. If a patients reported more than one AE within the same primary SOC, the patient will be counted only once with the greatest severity at the SOC level, where applicable. The AE will be presented in separate sections of ocular and non-ocular. For ocular then it will be presented by study eye, fellow eye, and any eye.

For the legal requirements of ClinicalTrials.gov and EudraCT, 2 required tables on treatment emergent AEs which are not SAEs with an incidence greater than 5% and on treatment emergent SAEs and SAEs suspected to be related to study treatment will be provided by system organ class and PT on the safety set population.

If for a same patient, several consecutive AEs (irrespective of study treatment causality, seriousness and severity) occurred with the same system organ class and PT:

- A single occurrence will be counted if there is ≤ 1 day gap between the end date of the preceding AE and the start date of the consecutive AE.

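### An adverse event with an unknown start year gets no start date, so read literally it drops out of the on-treatment AE, SAE and AESI tables and the AESI rate; the SAP should state a default classification

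*SAP*

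**What the plan says.** **The date rule.** SAP 5.1.2 states: "Therefore, if the AE year value is missing, the imputed AE start date is set to NULL". In the accompanying matrix all four cells of the missing-year row are NULL, even where the month is known, and all are labelled uncertain. The interim SAP has the same rule in its own 5.1.2.

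**The table filter.** SAP 2.9.1 says that the AE summary tables "will summarize only on-treatment events, with a start date during the on-treatment period". SAP 2.1.1 runs that period from the first injection "to 30 days after the date of the last actual administration of any study treatment". Protocol 12.5.5 applies the same start-date condition to the AESI tables.

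**The other uncertain dates.** Where the event year equals the treatment year and the month is missing or is the month of first treatment, SAP 5.1.2 says that "the imputed AE start date is set to one day after treatment start". Those events pass the filter.

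**What is recorded as an AE.** Protocol 10.1.1 counts only events that arise after consent: "Conditions that were already present at the time of informed consent should be recorded in the medical history of the patient". Screening and Baseline are one visit (SAP 1.1), with treatment intended that day or within 3 days (SAP 2.1.1).

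**Outputs that do not use an AE start date.** Exposure and vital signs do not, and deaths are selected on the time of death (SAP 2.9.2). Protocol 12.5.5.1 adds: "All collected AEs will be listed".

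**The concern.** A missing date cannot be shown to lie inside a period. If the programmer applies the filter as written, an AE without a start year is left out of the numerators of the AE, SAE and AESI tables. No section supplies a fallback. In this design a recorded AE of unknown onset is much more likely to follow the first injection than to precede it, so leaving it out makes the drug look slightly safer than it was. This matters most for the AESIs. Intraocular inflammation is the safety question behind protocol Amendments 2 to 4, and its counts will be small.

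**Working it through.** The documents give no figure to reproduce here. The check is whether the two rules, applied together, exclude the event, and how much one exclusion could matter.

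**Step 1: run the rules.** The example assumes one patient with a first dose on 10 Jun 2021 and a last dose on 14 Apr 2022. The on-treatment period then ends 30 days later, on 14 May 2022.

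| Recorded start | Date under SAP 5.1.2 | Passes the filter? |
|---|---|---|
| Year missing; month missing, Mar, Jun or Sep | NULL | No (all four) |
| 2021, month missing | 11 Jun 2021 | Yes |
| Jun 2021 | 11 Jun 2021 | Yes |
| Mar 2021 | 15 Mar 2021 | No |
| Sep 2021 | 1 Sep 2021 | Yes |
| 2022, month missing | 1 Jan 2022 | Yes |
| Mar 2022 | 1 Mar 2022 | Yes |
| Jun 2022 | 1 Jun 2022 | No |

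Every missing-year pattern fails. The other uncertain patterns (2021 with month missing, and Jun 2021) pass. The 2022 pattern with no month also passes, although its true onset could be later than 14 May 2022. The section therefore already accepts some doubt about the upper end of the period.

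**Step 2: which side of the first injection?** Consent and baseline are one visit and treatment normally follows within 3 days. Protocol 8.1 allows testing to be repeated within 14 days of first screening, so the gap can be longer for re-tested patients. Follow-up after that runs to Week 48 or 50. Few recorded AEs can predate the first dose.

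**Step 3: which side of the upper limit?** Protocol 9.1.1 keeps patients who stop treatment early in the study and collects their AEs to at least Week 48. With a last injection at Week 14 (day 98), the period ends on day 98 + 30 = 128. Up to day 336 that leaves 336 − 128 = 208 days, or 208/336 = 62%, off treatment. An undated event in such a patient could well be post-treatment. Protocol 12.5.5.1, unlike protocol 12.5.5 and SAP 2.1.1, extends the period to end of study if that is later; on that definition most of these days would count as on treatment.

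**Step 4: size.** If all 295 planned patients are treated, each patient whose only event in a category is lost lowers that incidence by 1/295 = 0.34 points (1/265 = 0.38 with 265 patients). Assuming 1 to 5 such patients, the loss is 0.34 to 5/295 = 1.69 points. Each lost AESI occurrence lowers the rate by 1000 divided by total injections. With three loading injections per patient, 3 × 295 = 885, this is 1000/885 = 1.13 per 1000, and less with more injections. The documents do not say how many AEs lack a start year.

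**The case against.** **The exclusion is an inference.** This is fair. The SAP never says that NULL-dated events are excluded; it only leaves them unable to meet the condition. The treatment-emergent definition in SAP 2.9.1 also has a second limb, "events present prior to start of study treatment but increased in severity based on PT", which needs no on-treatment start. That limb requires knowing that the event came before treatment, which a NULL date does not show, and the filter in the same section still asks for a start date.

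**Such events should hardly exist.** This largely stands. Start date is a required AE item (protocol 10.1.1), missing values are queried (protocol 11.2), and participation spans at most 50 weeks, so only one or two calendar years are possible. Suspected inflammation triggers immediate examination, which makes an undated inflammation event less likely still.

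**The different treatment is explained.** SAP 5.1.2 says that without a year the uncertainty is too great to impute a sensible date. That is a reason not to invent a date. It is not a reason to leave the event unclassified, since classifying it as treatment-emergent needs no date. The difference from the other uncertain cells is a weakness rather than a contradiction.

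**An on-treatment default could misattribute events.** This stands for patients followed after early discontinuation, some of them on another anti-VEGF drug (Step 3). A default that checks only for an end date before the first injection would be too loose.

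**A stronger reading of the size.** A reader might take the 3.2% (males) and 5.3% (females) inflammation frequencies in protocol 4.5, expect 295 × 0.032 = 9.4 to 295 × 0.053 = 15.6 cases, and infer that one lost case cuts the result by 1/15.6 = 6% to 1/9.4 = 11%. The documents do not support this as an expected bias. The frequencies are sex-specific, come from studies that ran to Week 96, and nothing shows that any inflammation event will lack a start year.

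**Conclusion.** The point holds within limits. Followed as written, SAP 5.1.2 and 2.9.1 together with protocol 12.5.5 remove an AE of unknown start year from the on-treatment AE, SAE and AESI incidence tables and from the AESI rate per 1000 injections. The direction is anti-conservative, and the section's other uncertain cells are handled the opposite way.

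A reader might infer that these events vanish from every safety output. They do not: the death, exposure and vital-sign summaries are untouched, and the protocol's listing of all collected AEs keeps them. The SAP's own listing sentence in 2.9.1 names treatment-emergent AEs and SAEs, so it is less clear there, and a listing does not restore an incidence in any case.

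The effect is at most 0.34 points per affected patient, assuming 295 treated. The number affected is unknown and probably near zero. This is a worthwhile, inexpensive correction to a stated rule, not evidence that the safety results are materially wrong.

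**What to change.** Change the missing-year rule in the final SAP, section 5.1.2. Leave the start date blank, but classify the event as treatment-emergent by default, unless other recorded data show otherwise. Such data would be an end date before the first injection, or a visit of first report or other record that places onset after the on-treatment period. Omit these events from the plots that need an onset time (SAP 2.9.1.1), and report how many there were. State also that each counts as one occurrence, because the gap rule for repeated events in SAP 2.9.1 needs a start date.

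The interim SAP has the same rule, but the final SAP (2.15) describes the interim analysis as already performed, so the final SAP is the place to act.

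The cost is a few lines of text and code. The downside is small: an occasional event that began before the first dose, or after the on-treatment period in a patient who stopped treatment early, may be counted. The reported number shows how far this could matter.

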5.1.3 Concomitant medication (CM)/procedure (PR) and and medical history (nAMD) date imputation

This algorithm is used when event is the partial start date of the concomitant medication.

The following table explains the notation used in the logic matrix. Please note that missing start dates will not be imputed.

	Day	Month	Year
Partial CM Start Date	Not used	MON	YYYY
Treatment Start Date (TRTSDT)	Not used	TRTM	TRTY

The following matrix explains the logic behind the imputation.

	MON MISSING	MON < TRTM	MON = TRTM	MON > TRTM
YYYY MISSING	(C2) Uncertain	(C1) Uncertain	(C1) Uncertain	(C1) Uncertain
YYYY < TRTY	(D) Before Treatment Start	(A) Before Treatment Start	(A) Before Treatment Start	(A) Before Treatment Start
YYYY = TRTY	(C2) Uncertain	(A) Before Treatment Start	(C1) Uncertain	(B) After Treatment Start
YYYY > TRTY	(E) After Treatment Start	(B) After Treatment Start	(B) After Treatment Start	(B) After Treatment Start

The following table is the legend to the logic matrix.

Relationship	
Before Treatment Start	Partial date indicates CMD start date prior to Treatment Start Date
After Treatment Start	Partial date indicates CMD start date after Treatment Start Date
Uncertain	Partial date insufficient to determine relationship of CMD start date relative to Treatment Start Date
Imputation Calculation	
(A)	15MONYYYY
(B)	01MONYYYY
(C1 or C2)	IF relative reference start = before treatment start THEN TRTSDT-1 ELSE IF relative reference start = ' ' THEN TRTSDT +1
(D)	01JULYYYY
(E)	01JANYYYY

Concomitant Medication End Date Imputation

If not ongoing then -

Imputed date = date part of CMENDTC, if complete date

Imputed date = min (completion/discontinuation visit date, DEC 31) , if month is missing, (C2, D, E)

Imputed date = min (completion/discontinuation visit date, last day of the Month) , if day is missing. (A, B, C1)

Concomitant Medication Date Flag

If not a complete date then

Y - If year of the imputed date is not equal to YYYY else M – If month of the imputed date is not equal to MON else D.

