5.1 Inclusion criteria

Eligible patients must meet **all** of the following criteria:

1. Patients must provide written informed consent before any study-related procedures are performed.
2. Patients must be 50 years of age or older at Screening/Baseline.

Study eye:

3. Active CNV lesions secondary to nAMD diagnosed < 18 months prior to Screening/Baseline that affect the central subfield, including retinal angiomatic proliferation (RAP) with a CNV component, confirmed by presence of active leakage from CNV seen by FA and sequelae of CNV, e.g. pigment epithelial detachment (PED), subretinal hemorrhage or sub-RPE hemorrhage, blocked fluorescence, or macular edema.
4. Previous treatment with only one licensed anti-VEGF drug (i.e. Lucentis[®], Eylea[®]) with a $\geq Q4$ and $\leq Q8$ treatment (treatment interval of 26 to 62 days inclusive) with licensed anti-VEGF (a minimal washout period of at least 4 weeks / 26 days is required). Patients must

have received at least 3 injections of this anti-VEGF in the 6 months prior to Screening/Baseline.

5. Presence of residual fluid (IRF or SRF that affects the central subfield under, as seen by OCT)
6. BCVA score must be ≤ 83 and ≥ 38 letters at an initial distance of 4 meters starting distance using Early Treatment Diabetic Retinopathy Study (ETDRS)-like visual acuity charts at Screening/Baseline.

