2.6.2 Supportive analyses

Subgroup analysis according to patient characteristics, like gender (male, female), age class (< 50, 50 - 65, 65 - 75, 75 - 85, \geq 85), Baseline fluids type (IRF, SRF, both), number of previous anti-VEGF injections (3, 4 - 6, 7 - 9 and \geq 10), interval (in week) since previous anti-VEGF injection (4, 5, 6, 7, 8) and time since nAMD diagnosis (2.5 - 5 month, 5 - 8 months, 8 - 11 months, 11 - 18 months and $>$ 18 months).

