5.1.4 Medical history date of diagnosis imputation

Completely missing dates will not be imputed. Partial dates of diagnosis will be compared to the treatment start date.

- If DIAG year < study treatment start date year and DIAG month is missing, the imputed DIAG date is set to the mid-year point (01JULYYYY).
- Else if DIAG month is not missing, the imputed DIAG date is set to the mid-month point (15MONYYYY).
- If DIAG year = study treatment start date year and (DIAG month is missing OR DIAG month is equal to study treatment start month), the imputed DIAG date is set to one day before study treatment start date.

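### Final SAP 5.1.3 places a year-only nAMD diagnosis date from the treatment year one day before or after first dose, which is implausible and falls below every time-since-diagnosis subgroup class

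*SAP*

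**What the plan says.** Final SAP 5.1.3 is headed "Concomitant medication (CM)/procedure (PR) and and medical history (nAMD) date imputation", and the SAP's table of changes records that procedures and nAMD history were added to this section. The final SAP has no other rule for diagnosis dates. The body was not adapted: "This algorithm is used when event is the partial start date of the concomitant medication".

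The matrix compares the partial date with the treatment start date (TRTSDT). A date in the treatment year with the month missing goes to cell C2; the same year and same month goes to C1. Both cells share one instruction: "IF relative reference start = before treatment start THEN TRTSDT-1", followed by "ELSE IF relative reference start = ' ' THEN TRTSDT +1". The text also says "Please note that missing start dates will not be imputed", yet the matrix assigns C1 or C2 to dates with no year.

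The interim analysis SAP had its own section 5.1.4. For a date in the treatment year with the month missing or equal to the treatment month, "the imputed DIAG date is set to one day before study treatment start date".

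The imputed date feeds two outputs. Final SAP 2.4.4 summarises time since diagnosis at baseline, continuously and in classes. Final SAP 2.6.2 uses it for a subgroup analysis of the primary endpoint, by "time since nAMD diagnosis (2.5 - 5 month, 5 - 8 months" and then 8 to 11, 11 to 18 and over 18 months. Protocol 12.4.4 also plans this subgroup.

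**The concern.** For a medication of unknown timing, a default start just after first dose is a defensible convention. Carried over to the disease that qualified the patient for the trial, it is not. Final SAP 2.1.1 itself gives time since diagnosis as its example of something that precedes treatment start. Protocol 5.1 requires diagnosis before Screening/Baseline, one previous licensed anti-VEGF drug, and that patients "have received at least 3 injections of this anti-VEGF in the 6 months prior to" Screening/Baseline.

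At stake are the integrity of one baseline variable and the completeness of one planned subgroup analysis. An affected patient would contribute a near-zero or negative time since diagnosis to the mean, minimum and quartiles, and would belong to none of the subgroup classes.

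**Working it through.** **Inputs**
- At least 3 prior injections, intervals of 26 to 62 days, washout of at least 26 days: Protocol 5.1, criterion 4.
- Diagnosis less than 18 months before baseline: Protocol 5.1, criterion 3.
- Imputation matrix: final SAP 5.1.3. Earlier rule: interim SAP 5.1.4.
- Subgroup classes: final SAP 2.6.2.
- Assumed for illustration: first dose on 12 October 2021; 30.4375 days per month.

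**1. Shortest plausible time since diagnosis.** Three injections span two intervals, and the washout follows: 2 × 26 + 26 = 78 days; 78 / 30.4375 = 2.56 months. The subgroup classes start at 2.5 months, which fits this floor.

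**2. Applying the rules to partial dates**

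| Partial diagnosis date | Final SAP | Time since diagnosis | Class (2.6.2) | Interim SAP |
|---|---|---|---|---|
| 2021, month missing, reference blank | 13 Oct 2021 | −1 day (−0.03 months) | none | 11 Oct 2021, +1 day, none |
| 2021, month missing, flagged before | 11 Oct 2021 | +1 day (0.03 months) | none | same |
| March 2021 | 15 Mar 2021 | 211 days (6.9 months) | 5–8 | same |
| 2020, month missing | 1 Jul 2020 | 468 days (15.4 months) | 11–18 | same |
| September 2020 | 15 Sep 2020 | 392 days (12.9 months) | 11–18 | same |

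The trouble is confined to the treatment-year case. Earlier years, and earlier known months in the treatment year, already receive sensible mid-month or mid-year dates.

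**3. Which cell matters.** C1 (same year and month) cannot be true for a patient who meets the criteria, because 78 days is longer than any month. The realistic route is C2, the year-only date.

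**4. Size of the error in the example.** A true diagnosis in 2021 lies between 1 January (284 days before first dose, 9.3 months) and 26 July (78 days before, 2.56 months). The rule gives +1 or −1 day, so it is wrong by at least 78 − 1 = 77 days.

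**5. How often, under an assumption.** The documents do not give the number of partial dates. Suppose first-dose dates are uniform over a 365-day year and time since diagnosis is uniform over 78 to 547 days (470 values). Of 365 × 470 = 171,550 combinations, 1 + 2 + … + 287 = 41,328 have diagnosis and first dose in the same year: 41,328 / 171,550 = 24%. About a quarter of year-only dates would then reach C2. This is a share of year-only dates, not of patients.

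**6. Result of a bounded rule.** If the first anti-VEGF injection was on 26 July 2021, the midpoint from 1 January is 206 / 2 = 103 days later, 14 April 2021. That is 181 days before first dose, or 5.9 months, class 5–8. The error is at most 103 days (3.4 months) either way.

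**The case against.** The best case against the point has several parts, and much of it limits what can be claimed.

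- **Diagnosis after first dose.** A reader might infer that the plan puts diagnosis after first dose as a matter of course. It does so only when the relative-reference field is blank, and the documents do not show whether the nAMD history page has that field. Conditions present at consent belong in medical history (Protocol 10.1.1), so the before-treatment branch is a natural reading. That branch still gives 0.03 months and no class.
- **Blaming the merger.** A reader might infer that dropping the interim rule caused the subgroup loss. It did not: the interim rule gave the same minus 1 day, and the final SAP keeps its mid-month and mid-year imputations.
- **Dates with no year.** These might seem to be moved to first dose as well. The matrix suggests it, but the text on missing start dates points the other way, so the claim is not secure.
- **A hard 78-day floor.** It holds for patients who meet the criteria. Those whose previous anti-VEGF interval was out of range (INCL04c) stay in the FAS and may have somewhat less. Having fewer than 3 injections (INCL04b) excludes a patient from the FAS, so a value near zero remains implausible there.
- **Every classification lost.** The lowest baseline class in final SAP 2.4.4 is written < 2.5 - 5 and might absorb such values. The classes in 2.6.2 do not.
- **Scope.** The body text of 5.1.3 names only medication, so one could argue that nAMD dates are not covered. The heading and table of changes say otherwise, and on the narrow reading no diagnosis-date rule exists at all.
- **Rarity.** Date of diagnosis is a baseline item (Protocol 8.2), missing values are queried (11.2), and adherence to the inclusion criteria is fully verified (11.3). Few records should be affected. This limits the importance of the point but does not make the rule right.

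**Conclusion.** The point holds as a minor error in a stated rule. For a year-only diagnosis date in the treatment year, final SAP 5.1.3 returns a time since diagnosis of about zero, on one side of first dose or the other, where about 2.56 months is the minimum for a patient meeting the criteria. The patient then falls outside all classes of the planned subgroup analysis, and the continuous baseline summary takes in a false value. The primary proportion does not use this date and is unaffected.

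This rests on reading the heading and table of changes as bringing nAMD dates under the algorithm. It does not depend on the blank-reference branch, because both branches fail. The number of affected records is unknown and probably small.

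**What to change.** Give nAMD diagnosis its own short rule in the final SAP:

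1. Keep mid-month imputation when year and month are known, and mid-year imputation when only an earlier year is known.
2. For a year-only date in the treatment year, use the midpoint between 1 January and the recorded date of the first anti-VEGF injection.
3. Cap every imputed diagnosis date at that first injection.
4. Leave dates with no year missing.
5. Align the heading, body text and matrix of 5.1.3 with this, including the treatment of dates with no year.

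Returning to the interim rule without steps 2 and 3 would remove the date after first dose but not the loss from the subgroups. The cost is a few lines of SAP text and code. The first-injection date is already collected at baseline (Protocol 8.2) and listed (final SAP 2.5.4), so no new data are needed.
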